#### During study the sponsor shall:

Provide AZ Individual Case Safety Reports (ICSRs), initial and follow-up information, as they occur for related SAEs:

- Unblinded Suspected Unexpected Serious Adverse Reactions (SUSARs)
- Suspected Serious Adverse Reactions (SSARs)

Accept to be contacted by AZ regarding any safety reports including contradictory information or missing data. Sponsor is expected to respond to any such queries in a timely manner.

Provide AZ with any emerging safety issues, unanticipated problems or actions as a result of a safety signal with AZ study drug within 24 hours of knowledge.

Provide AZ with a copy of their DSUR (Development Safety Update Report) in those cases the safety reference information used by the sponsor, is inconsistent with AZ IB and Local Label. In these rare circumstances, it is provided for informational purposes only. It is made available in parallel of it being distributed externally.

#### 9.2.3. Suspected unexpected serious adverse reactions (SUSARs)

Adverse reactions are all untoward and unintended responses to an investigational product related to any dose administered.

Unexpected adverse reactions are SUSARs if the following three conditions are met:

- 1. the event must be serious (see chapter 9.2.2);
- 2. there must be a certain degree of probability that the event is a harmful and an undesirable reaction to the medicinal product under investigation, regardless of the administered dose;
- 3. the adverse reaction must be unexpected, that is to say, the nature and severity of the adverse reaction are not in agreement with the product information as recorded in:
  - Summary of Product Characteristics (SPC) for an authorized medicinal product;
  - Investigator's Brochure for an unauthorized medicinal product.

The sponsor will report expedited the following SUSARs through the web portal *ToetsingOnline* to the METC

 SUSARs that have arisen in other clinical trials of the same sponsor and with the same medicinal product, and that could have consequences for the safety of the subjects involved in the clinical trial was assessed by the METC.

The remaining SUSARs are recorded in an overview list (line-listing) that will be submitted once every half year to the METC. This line-listing provides an overview of all SUSARs from the study medicine, accompanied by a brief report highlighting the main points of concern. The expedited reporting of SUSARs through the web portal Eudravigilance or ToetsingOnline is sufficient as notification to the competent authority.

The sponsor will report expedited all SUSARs to the competent authorities in other Member States, according to the requirements of the Member States.

The expedited reporting will occur not later than 15 days after the sponsor has first knowledge of the adverse reactions. For fatal or life-threatening cases, the term will be maximal 7 days for a preliminary report with another 8 days for completion of the report.

There will be three sets of emergency code breaks, one set will be retained by the project leader, one set will be retained by the principal investigator and a set will be forwarded to the pharmacy. The blinded emergency code break contains the details of drug treatment. In an emergency, the code can be unblinded to identify the treatment given to that subject. Unblinding is not to be performed for any reason, other than an emergency where unblinding is required. When the Investigator removes the scratch-off covering he/she must note the date, time and reason for removing it and record this information in the Comments section of the CRF/ on the code-break card (source data). He/she must also immediately inform the project leader and the principal investigator that the code has been broken. Even though the code is broken, any blood samples for safety or pharmacodynamic assessments will continue to be drawn, for at least 24hr following the last dose as long as doing so will not compromise subject welfare.

It is the responsibility of the Investigator to ensure that there is a procedure in place to allow access to the code break cards in case of emergency. Study drug must be discontinued after unblinding, but the subject will be followed until resolution of the adverse event. At the conclusion of the study, the occurrence of any emergency code breaks will be determined after return of all code break reports.

#### 9.3. Annual safety report

In addition to the expedited reporting of SUSARs, the sponsor will submit, once a year throughout the clinical trial, a safety report to the accredited METC,

competent authority, and competent authorities of the concerned Member States.

This safety report consists of:

a list of all suspected (unexpected or expected) serious adverse reactions, along with an aggregated summary table of all reported serious adverse reactions, ordered by organ system, per study;

a report concerning the safety of the subjects, consisting of a complete safety analysis and an evaluation of the balance between the efficacy and the harmfulness of the medicine under investigation.

#### 9.4. Follow-up of adverse events

All AEs will be followed until they have abated, or until a stable situation has been reached. Depending on the event, follow-up may require additional tests or medical procedures as indicated, and/or referral to the general physician or a medical specialist. SAEs need to be reported till end of study within the Netherlands, as defined in the protocol.

#### 9.5. [Data Safety Monitoring Board (DSMB) / Safety Committee]

A DSMB is not needed for this study, given the extensive experience with dapagliflozin in the enrolled population (safety data from clinical trials available in more than 30,000 patients).

#### 10. STATISTICAL ANALYSIS

#### 10.1. Primary study parameter(s)

The change from baseline in UACR will be calculated using the values collected at day 5, 6 and 7 of each treatment and wash-out period. Because of the skewed distribution UACR will be log-transformed before analysis. The geometric mean of these 3 values (at baseline to end of treatment) will be calculated as log(UACRend/UACRbaseline) and the geometric mean change from baseline will be determined.

The study has two cycles for two treatment periods (dapagliflozin and placebo). For calculation of response, the difference in UACR change between dapagliflozin and placebo will be calculated during the first and second cycle. To this end a linear mixed effects model with random intercepts and random slopes for treatment will be used to determine the response during each period. Fixed effects include treatment sequence, and treatment cycle. Baseline log transformed UACR may be added as covariate. Appropriate contrasts will be implemented to assess the placebo substracted response during the first and second cycle and to correlate the placebo adjusted UACR responses to dapagliflozin (fitted on the log-scale) during the two treatment periods. The variance-covariance pattern of the mixed effects model is assumed to be unstructured. If the model does not converge less stringent models will be considered.

To determine if there is within individual variation in treatment response, we will fit a linear mixed model with correlated random intercepts and random slopes for treatment and include treatment period as a fixed effect. Subsequently, we will compare (using a maximum-likelihood ratio fit test) this model against a random intercept only model with treatment and treatment period as fixed effects.

In an additional supportive analysis, we will also dichotomize response. If the placebo adjusted difference in both cycles is greater than 20% in favor of dapagliflozin (using the linear mixed effects model), the patient will meet the response definition. We will then perform a McNemar test for the proportion of concordant response (response during the two cycles or no response during

the two cycles) versus discordant responses (i.e., response first cycle and no response second cycle or vice versa). The proportion of responders will also be calculated if UACR response is defined as a 30% difference in UACR. The 20% and 30% response threshold is based on prior studies of UACR response.

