### 4.4. Sample size calculation

The sample size for this study is based on the hypothesis that the response to dapagliflozin is reproducible upon re-exposure and thus correlates between the first and second exposure while no correlation will be detected during placebo patients. A prior retrospective study found that during intervention in the reninangiotensin-system responses in proteinuria correlate with correlation coefficients ranging between 0.7 to 0.9.9 Since this was a retrospective study, we assume a more conservative correlation coefficient of 0.6. A sample size of 20 patients provides >80% power (alpha 0.05) to detect a correlation coefficient of 0.6.

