### 8.5. Replacement of individual subjects after withdrawal

Patients that meet the inclusion criteria will be invited for participation in the study. When a patient agrees to participate in the study, patients will be invited for screening and informed consent is signed. After the screening visit, eligible patients will proceed to the second visit. When patients decide to withdraw after start of the treatment period, they will be replaced so that twenty patients will complete the full study protocol.

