#### 5.1. Analysis of primary and secondary study outcome

The change from baseline in UACR will be calculated using the values collected at day 5, 6 and 7 of each treatment and wash-out period. Because of the skewed distribution UACR will be log-transformed before analysis. The geometric mean of these 3 values (at baseline to end of treatment) will be calculated as log(UACRend/UACRbaseline) and the geometric mean change from baseline will be determined.

The study has two cycles of two treatment periods (dapagliflozin and placebo). For the calculation of response, the difference in log-transformed UACR change between dapagliflozin and placebo will be calculated during the first and second cycle. Patient level Bayesian analysis:

First, a Bayesian analysis will be conducted to calculate the posterior probability of dapagliflozin producing a clinically meaningful response on UACR within each individual patient relative to placebo for both treatment cycles combined. Thus for every patient, data of each cycle is combined and expressed in the form of a likelihood function with non-informative priors to calculate the posterior distribution. A clinically meaningful response on UACR is defined as the placebo subtracted percentage UACR change during the first and second cycle with different thresholds of 10%, 20% or 30% reduction in UACR. Population level Bayesian hierarchical analysis:

Subsequently, individual patient results on UACR will be combined to conduct a Bayesian hierarchical analysis to calculate the posterior probabilities of a clinically meaningful response at the population level (10%, 20%, and 30%). Therefore, responses on UACR from each patient will be aggregated into a sample mean and variance, assuming a normal distribution centred around the patient's true mean effect and variance. The Bayesian hierarchical model is defined as:

$$Y_{ij} \sim N(\alpha_i + \beta_i X_{ij}, \sigma_i).$$

Were  $Y_{ij}$  is the placebo subtracted UACR response for the  $i^{th}$  subject at time j and is described by  $x_{ij}$  ( $x_{ij}=1$  if treated with dapagliflozin; =0 if placebo treated). The subject specific intercept and slope were modelled as  $a_i \sim N(a_0, \tau_a^2)$  and  $\beta_i \sim N(\beta_0, \tau_\beta^2)$  respectively. Again, we used non-informative prior for  $a_0$ ,  $\beta_0$ ,  $\tau_a^2$ ,  $\tau_\beta^2$ ,  $\sigma_i$ .

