#### Frequentist linear mixed effects analysis:

In addition to this Bayesian approach, we will also utilize a frequentist approach to determine the response on UACR during each period. To estimate this response a linear mixed effects model with random intercepts and random slopes for treatment will be used. Fixed effects include treatment sequence, and treatment cycle. Baseline log-transformed UACR may be added as covariate. Appropriate contrasts will be implemented to assess the placebo subtracted response during the first and second cycle and to correlate the placebo adjusted UACR responses to dapagliflozin (fitted on the log-scale) during the two treatment periods. The variance-covariance pattern of the mixed effects model is assumed to be unstructured. If the model does not converge less stringent models will be considered.

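### UACR response is scored as change from period baseline with baseline adjustment optional or absent; mandatory within-patient adjustment would be more precise, by an amount the documents cannot fix

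*Combined protocol and SAP*

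**What the plan says.** Protocol 10.1 takes UACR from days 5, 6 and 7 of each treatment and wash-out period and forms the log ratio of end to baseline. The placebo change is then subtracted from the dapagliflozin change in each cycle. SAP 5.1 repeats this: "the difference in log-transformed UACR change between dapagliflozin and placebo will be calculated during the first and second cycle".

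On adjustment, protocol 10.1 says "Baseline log transformed UACR may be added as covariate", and the SAP's frequentist mixed model says "Baseline log-transformed UACR may be added as covariate". Neither gives a rule for when the covariate enters or says which baseline is meant. The SAP's two Bayesian analyses, which come first in section 5.1, and its fixed-effect heterogeneity model list no baseline term. Protocol 10.2 analyses the secondary outcomes in the same way as the primary.

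Urine is collected on days -7, -3, -2 and -1 and on days 3, 5, 6 and 7 of each wash-out (protocol section 3, Measurements), so every treatment period has a baseline. Protocol 10.1 does not say which run-in days serve Period 1.

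The sample size (protocol 4.4, SAP 3.2) rests on the correlation between first and second responses: "A sample size of 20 patients provides >80% power (alpha 0.05) to detect a correlation coefficient of 0.6". No standard deviation, baseline correlation or response definition enters it.

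**The concern.** In a cross-over the patient's own level cancels when placebo is subtracted from dapagliflozin. Each change score also brings in the error of a three-day baseline mean with its coefficient fixed at 1. Unless the end value follows the baseline one-for-one within a patient, that coefficient is too large and the surplus is noise.

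Noise in the one-cycle response directly weakens the between-cycle correlation that the trial is powered to detect. It also blurs each patient's own estimate, and with it the probability or classification of a 10%, 20% or 30% reduction. Separately, the permissive wording leaves a modelling choice open until the data have been seen.

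**Working it through.** **The plan's own figure.** Inputs from protocol 4.4: n = 20, alpha 0.05 (taken as two-sided; not stated), r = 0.6. Withdrawals need no allowance because "they will be replaced so that twenty patients will complete the full study protocol" (protocol 8.5).

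- n = ((1.960 + 0.842)/atanh(0.6))² + 3 = (2.802/0.6931)² + 3 = 19.3, rounded up to 20.
- Power at n = 20 = Φ(0.6931 × √17 − 1.960) = Φ(0.898) = 81.5%.

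The stated figure reproduces.

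**Noise in a one-cycle response.** Let s² be the within-patient variance of a three-day log mean, and rho the within-patient correlation between a period's baseline and its end value. Neither is in the documents. Assume no other correlation between weeks within a patient.

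- Change scores: each has variance 2s²(1 − rho), so the difference of two has 4s²(1 − rho).
- End values adjusted for the within-patient baseline: each has s²(1 − rho²), so the difference has 2s²(1 − rho²).
- Ratio, change to adjusted: 4(1 − rho)/[2(1 − rho)(1 + rho)] = 2/(1 + rho).
- End values alone: 2s².

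**Effect on the correlation.** With true between-patient variance of response τ², the expected correlation between cycles is τ²/(τ² + noise). If change scores give 0.6, then τ² = 1.5 × 4s²(1 − rho) = 6s²(1 − rho). The adjusted correlation is then 6/(6 + 2(1 + rho)) = 3/(4 + rho).

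| rho | change noise /s² | adjusted noise /s² | factor | adjusted r | power, n = 20 |
|---|---|---|---|---|---|
| 0 | 4.00 | 2.00 | 2.00 | 0.750 | 98.0% |
| 0.3 | 2.80 | 1.82 | 1.54 | 0.698 | 94.5% |
| 0.5 | 2.00 | 1.50 | 1.33 | 0.667 | 91.3% |
| 0.8 | 0.80 | 0.72 | 1.11 | 0.625 | 85.6% |

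If 0.6 instead describes adjusted responses, change scores give r = 3(1 + rho)/(3(1 + rho) + 4) = 0.429, 0.494, 0.529 and 0.574, with power 47%, 61%, 68% and 77%.

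**Simulation.** With 20 patients, two cycles, assumed log SDs of 1.2 between and 0.25 within patients, and the slope estimated from the data, power for change scores against within-patient adjustment was 83% v 98%, 84% v 94%, 84% v 92% and 84% v 86% at rho 0, 0.3, 0.5 and 0.8.

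**Does the optional covariate recover this?** Under the same assumed SDs, raw period baseline was added to a mixed model for change with random intercepts and treatment slopes. The fitted slope on baseline averaged -0.08, -0.04, -0.04 and -0.01, against the -1.0, -0.7, -0.5 and -0.2 needed. The change score has already removed the patient's level, so the slope is driven by the wide between-patient spread. When the patient's mean baseline was entered as well, the recovered slopes of end value on baseline were 0.02, 0.29 and 0.63 for true rho of 0, 0.3 and 0.6.

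**The case against.** The strongest reply is that the plan meets its own target. If 0.6 refers to change-score responses, power is above 80% as stated, and adjustment is an efficiency gain rather than a repair. Since rho is unknown, the gain may be only from 81.5% to 85.6%. The Fisher-z figures also describe a simple correlation of one-cycle responses, whereas the plan takes its responses from mixed-model contrasts. All of this stands, and it limits what can be said about size.

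A reader might infer several stronger points that the documents do not support.

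- *The power statement is wrong.* It is conditional on 0.6, and the plan does not tie 0.6 to a response definition.
- *Subtracting baseline always adds noise.* Against end values alone that is true only for rho below 0.5. At rho 0.8 the change score has 0.8s² against 2s². The general advantage belongs to within-patient adjustment.
- *Making the covariate compulsory is enough.* In raw form it recovers almost none of the loss.
- *The baseline imports carry-over.* The protocol summary reports that effects returned to baseline 4 days after stopping in a prior study, and the wash-out baseline uses days 5 to 7. An adjusted model would also pass on part of any contamination.

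Finally, if baseline meant one pre-study value, it would cancel from the placebo-subtracted contrast and the noise argument would fall away. The reference in protocol 10.1 to each wash-out period points to a period-specific baseline, but the text should say so.

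**Conclusion.** The point holds as a matter of precision and pre-specification. Whenever rho is below 1, change scores are less precise than within-patient adjustment for the period baseline, by a variance factor of 2/(1 + rho): from 2.00 at rho 0 to 1.11 at rho 0.8. Because the trial depends on a correlation in 20 patients with little margin above 80%, the gain is worth taking. Its size cannot be settled from the documents. The power figures depend on the assumed rho, on independence between weeks otherwise, on 0.6 applying to change scores, and on a two-sided 5% test. The undefined, optional covariate needs resolving whatever rho turns out to be.

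**What to change.** In protocol 10.1 and SAP 5.1:

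1. Define baseline for each period as the mean log UACR of days 5 to 7 of the preceding wash-out, and of run-in days -3 to -1 for Period 1. Name the corresponding days for each secondary outcome.
2. Replace the permissive wording with mandatory adjustment in within-patient form: the period baseline together with the patient's mean baseline, or the per-cycle baseline contrast.
3. Specify this in the patient-level and hierarchical Bayesian models, the frequentist mixed model, the heterogeneity models and the secondary-outcome models. In the fixed-effect heterogeneity model the subject terms already absorb the patient's mean, so the period baseline suffices. In the patient-level analysis use a slope common to all patients, since one patient supplies only four treatment periods.
4. The endpoint may stay as log change. With the period baseline in the model, change and end value give the same treatment estimate.

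The cost is a wording change to both documents, made before unblinding, and one or two degrees of freedom. No new data are needed.

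### The supportive McNemar test in Protocol 10.1 cannot compare concordant with discordant responses, so it gives no evidence on whether response is reproducible

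*Combined protocol and SAP*

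**What the plan says.** The hypothesis behind the design (Protocol 4.4) is that "the response to dapagliflozin is reproducible upon re-exposure and thus correlates between the first and second exposure". Protocol 10.1 addresses it mainly through a mixed model, from which the placebo-adjusted log-UACR responses of the two cycles are correlated, and through a likelihood-ratio comparison of a random-slope with a random-intercept model.

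It then adds: "In an additional supportive analysis, we will also dichotomize response". A patient counts as a responder under this condition: "If the placebo adjusted difference in both cycles is greater than 20% in favor of dapagliflozin", with the mixed model supplying the difference. The test follows: "We will then perform a McNemar test for the proportion of concordant response" (response in both cycles or in neither) "versus discordant responses (i.e., response first cycle and no response second cycle or vice versa". For the higher threshold only a proportion is planned: "The proportion of responders will also be calculated if UACR response is defined as a 30% difference in UACR".

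SAP section 5, including 5.1 and its frequentist and heterogeneity subsections, contains neither a McNemar test nor any other concordance analysis. It uses thresholds of 10%, 20% and 30% in posterior probabilities that combine both cycles. It does not say that the protocol's test has been dropped.

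**The concern.** The sentence asks whether agreement between cycles outweighs disagreement. McNemar's test asks whether the responder rate moved between cycles. The patients who agree, who carry the information on reproducibility, do not enter the statistic.

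A non-significant result could therefore be reported as support for repeatable response when it shows only that the two discordant counts were similar. A significant result could be read as non-reproducibility when it shows a shift in rate. The definition adds a second difficulty: response is defined across both cycles together, while the table needs a status for each cycle.

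**Working it through.** **1. The plan's own figure.** Protocol 4.4 states: "A sample size of 20 patients provides >80% power (alpha 0.05) to detect a correlation coefficient of 0.6". By the Fisher z approximation, taking alpha as two-sided (the plan does not say), power = Φ(atanh(0.6) × √(20 − 3) − 1.960) = Φ(0.6931 × 4.1231 − 1.960) = Φ(0.898) = 81.5%. The figure reproduces. It belongs to the correlation; the plan gives no figure for the McNemar test. Under Protocol 8.5 withdrawn patients are handled thus: "they will be replaced so that twenty patients will complete the full study protocol". So n = 20 is used below.

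**2. Formulas.** Let a = response in both cycles, b = cycle 1 only, c = cycle 2 only, d = neither.
- McNemar, asymptotic: (b − c)² / (b + c). Exact: binomial test of b out of b + c at 0.5. Neither contains a or d.
- Agreement: po = (a + d)/n.
- Chance agreement: pe = [(a + b)(a + c) + (c + d)(b + d)]/n².
- Kappa = (po − pe)/(1 − pe).

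**3. Hypothetical tables, n = 20.** The documents give no expected responder rate, so these are illustrations.

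| a/b/c/d | Agreement | Kappa | Exact McNemar p |
|---|---|---|---|
| 10/0/0/10 | 100% | 1.0 | 1.0 by convention (asymptotic: 0/0) |
| 8/2/2/8 | 80% | 0.6 | 1.0 |
| 5/5/5/5 | 50% | 0 | 1.0 |
| 2/8/8/2 | 20% | −0.6 | 1.0 |
| 0/10/10/0 | 0% | −1.0 | 1.0 |
| 7/6/0/7 | 70% | 0.45 | 0.031 |
| 14/6/0/0 | 70% | 0 | 0.031 |
| 0/6/0/14 | 70% | 0 | 0.031 |

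In the last three rows p = 2 × 0.5⁶ = 0.031, however the 14 concordant patients are split.

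**4. Rejection rates.** 20,000 simulated trials of 20 patients, bivariate normal responses, the same assumed responder rate in both cycles, 5% level:

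| Assumed rate | Test | Latent correlation 0 | 0.3 | 0.6 | 0.9 |
|---|---|---|---|---|---|
| 50% | McNemar, exact | 2.3% | 1.9% | 1.1% | 0.1% |
| 50% | McNemar, asymptotic | 4.2% | 4.3% | 4.6% | 2.8% |
| 50% | Fisher, one-sided | 2.0% | 10.8% | 39.6% | 92.3% |
| 70% | Fisher, one-sided | 1.6% | 8.8% | 32.3% | 84.1% |

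McNemar does not gain power as reproducibility improves, and the exact version rejects less often. A test that uses all four cells does respond to reproducibility, though weakly at a correlation of 0.6.

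**5. A simple count is no substitute.** Suppose the intention was a binomial test of concordant against discordant counts at 50%. With independent cycles and a 70% responder rate, chance alone gives agreement of 0.7² + 0.3² = 0.58. In the simulation that test found agreement above 50% in 9.1% of trials with no correlation, against 2.2% at a 50% responder rate. The table 16/2/2/0 shows the same problem: agreement is 80%, but pe = (18 × 18 + 2 × 2)/400 = 0.82 and kappa = −0.02/0.18 = −0.11.

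**6. Where each cycle's status comes from.** The model has one random treatment slope per patient. Without a treatment-by-cycle term, the fitted dapagliflozin-minus-placebo difference for a patient is the same in both cycles, so b and c would be empty by construction. The contrasts are not specified closely enough to tell whether such a term is included.

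**7. Precision of kappa.** For 8/2/2/8 the simple large-sample standard error is √[0.8 × 0.2 / (20 × 0.5²)] = 0.179. The 95% interval is 0.6 ± 1.96 × 0.179, or about 0.25 to 0.95.

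**The case against.** The best defence is that little hangs on this sentence. The protocol labels the analysis supportive. Delete it, and the objectives, the sample size, the between-cycle correlation and the likelihood-ratio test are unchanged. The SAP already omits it. All of this stands and sets the weight of the point.

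A reader might infer that the trial's claim of reproducible response rests on an invalid test. The documents do not support that, because the correlation and the mixed-model comparison carry the claim. Nor is the test always impossible under perfect agreement: that is true of the asymptotic statistic, while exact software may return p = 1. The result p = 1.0 under complete disagreement also depends on the two discordant cells being equal.

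The obvious replacement has limits too. A two-sided Fisher test is as significant for 0/10/10/0 as for 10/0/0/10 (p = 0.00001 for each), so it would not by itself show agreement. One-sided, it has only about 32–40% power at a latent correlation of 0.6. These limits argue for estimation over testing. They do not make McNemar suitable, and the omission from the SAP does not withdraw the protocol text.

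**Conclusion.** The point holds. As written, the test cannot make the comparison described: its p-value is unrelated to agreement, with p = 1.0 across tables whose kappa runs from +1 to −1 and p = 0.031 for tables whose kappa is 0 or 0.45. That follows from the formula and needs no assumption. The simulated rejection rates do rest on assumptions: responder rates of 50% and 70%, equal in both cycles, and bivariate normal responses.

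The consequence is confined to a supportive analysis in the protocol and to its mismatch with the SAP. It should be fixed, but it does not threaten the main analysis of reproducibility or the sample size.

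**What to change.** Either of two routes resolves it.

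**Replace.** In Protocol 10.1:
- Define response separately for each cycle, classified from that cycle's own placebo-subtracted change in log UACR and not from a fitted slope shared by both cycles.
- Replace the McNemar sentence with the cycle-1 by cycle-2 table, the agreement proportion and Cohen's kappa with a 95% confidence interval at the 20% threshold, optionally also at 30%. Kappa is undefined if all patients fall in one concordant cell; the table and agreement would then stand alone.
- If a test of association is wanted, make it one-sided for positive association and label it low-powered at n = 20.
- Keep McNemar, if at all, only as a check for a shift in responder rate between cycles.
- Add the same text to SAP 5.1, as a supportive analysis.

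**Delete.** Remove the sentence from the protocol and state in the SAP that the concordance analysis is dropped.

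The cost is a few sentences in the protocol and SAP. No extra data, visits or patients are needed, and the sample size stays as it is.
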